**NOTES :**

- Unless otherwise specified, the baseline definitions specified in Section 11.5.2.1. Baseline Definitions will be used for derivations for endpoints / parameters and indicated on summaries and listings.
- Unless otherwise stated, if baseline data is missing no derivation will be performed and will be set to missing.
- The baseline definition will be footnoted on all change from baseline displays.

**11.5.3. Reporting Process & Standards**

Reporting Process
Software

 
• Version 6.2.1 (or higher) of WinNonlin will be used to determine PK parameters.
 
• Version 9.4 of SAS software will be used to create output displays (TLFs).
 

Analysis Dataset

 
• Analysis datasets will be created according to CDISC standards (SDTM IG Version 3.1 or higher & AdAM IG Version 1.1.)
 
• For creation of ADaM datasets (ADCM/ADAE), the same version of dictionary datasets will be implemented for conversion from SI to SDTM.
 

Generation of RTF Files

 
• RTF files will be generated for outputs (TLFs).
 

Reporting Standards
General

 
• The current GSK Integrated Data Standards Library (IDSL) will be applied for reporting, unless otherwise stated:                             
 
○ 4.03 to 4.23: General Principles
 
○ 5.01 to 5.08: Principles Related to Data Listings
 
○ 6.01 to 6.11: Principles Related to Summary Tables
 
○ 7.01 to 7.13: Principles Related to Graphics
 
 
 
• For placebo group, pooling of placebo subjects with each part is considered a general report rule, unless otherwise specified. All summary tables are for each part and all listings are for both parts combined into one, unless otherwise specified.
 

Formats

 
• All data will be reported according to the actual treatment the subject received unless otherwise stated.
 
• GSK IDSL Statistical Principles (5.03 & 6.06.3) for decimal places (DP's) will be adopted for
 

Reporting Standards	
reporting of data based on the raw data collected.	

 
Numeric data will be reported at the precision collected on the eCRF and laboratory reports.
 
	
Planned and Actual Time	

 
Reporting for tables, figures and formal statistical analyses: 
 
Planned time relative to dosing will be used in figures, summaries, statistical analyses of concentration and lab data unless otherwise stated.
 
Actual time relative to dosing will be used to determine PK parameters, unless otherwise stated.
 
The impact of any major deviation from the planned assessment times and/or scheduled visit days on the analyses and interpretation of the results will be assessed as appropriate.
 
 
 
Reporting for Data Listings: 
 
Planned and actual time relative to study drug dosing will be shown in listings (Refer to IDSL Statistical Principle 5.05.1).
 
Unscheduled or unplanned readings will be presented within the subject's listings.
 
Visits outside the protocol defined time-windows (i.e. recorded as protocol deviations) will be included in listings but may be omitted from figures, summaries and statistical analyses if the deviation is great enough, according to Section 11.1.
 
 
 
	
Unscheduled Visits	

 
Unscheduled visits will not be included in summary tables or figures.
 
All unscheduled visits will be included in listings.
 
	
Descriptive Summary Statistics	
Continuous Data	Refer to IDSL Statistical Principle 6.06.1
Categorical Data	N, n, frequency, %
Reporting of Pharmacokinetic Concentration Data	
Descriptive Summary Statistics	Refer to IDSL Statistical Principle 6.06.1 Assign zero to NQ (BLQ) values (Refer to GUI_51487 for further details)
Reporting of Pharmacokinetic Parameters	
Descriptive Summary Statistics (Log Transformed)	N, n, geometric mean, 95% CI of geometric mean, standard deviation (SD) of logged data and [between and or within] geometric coefficient of variation (CV b/w (%)) will be reported, based on one-sample analysis: [1] $CV_b (\%) = \sqrt{\exp(SD^2) - 1} * 100$ (SD = SD of log transformed data) [2] $CV_w (\%) = \sqrt{\exp(MSE) - 1} * 100$ (MSE = mean square error from mixed effect model of loge-transformed data).
Parameters Not Log Transformed	Parameters t max , Ae, and CL r will not be transformed.
Summary Tables	All derived PK parameters which were listed in Table 7 in Section 8.1.3 above.
Listings	Will include, for each subject PK profile, the first point and number of points

Reporting Standards	
	used in the determination of lambda_z.
Figures	

• Will include Plasma PK Concentration-Time Plots (Linear and Semi-log)

○ Individual (PK16a)

○ Mean (PK17)

○ Median (PK18)

• Box plot of PK parameters vs. Treatment

## 11.6. Appendix 6: Derived and Transformed Data

### 11.6.1. General

#### Multiple Measurements at One Time Point

- Mean of the measurements will be calculated and used in any derivation of summary statistics but if listed, all data will be presented.
- If there are two values within a time window the value closest to the target day for that window will be used. If values are the same distance from the target then the mean will be taken.
- Subjects having both High and Low values for Normal Ranges at any post-baseline visits for safety parameters will be counted in both the High and Low categories of “Any visit post-baseline” row of related summary tables. This will also be applicable to relevant Potential Clinical Importance summary tables.

#### Study Day

- Calculated as the number of days from randomisation date:
  - Ref Date = Missing → Study Day = Missing
  - Ref Date < Randomisation Date → Study Day = Ref Date – Randomisation Date
  - Ref Date ≥ Randomisation Date → Study Day = Ref Date – (Randomisation Date) + 1

### 11.6.2. Study Population

#### Demographics

##### Age

- GSK standard IDSL algorithms will be used for calculating age where birth date will be imputed as follows:
  - Any subject with a missing day will have this imputed as day ‘15’.
  - Any subject with a missing date and month will have this imputed as ‘30th June’.
- Birth date will be presented in listings as ‘YYYY’.

##### Body Mass Index (BMI)

- Calculated as **Weight (kg) / [Height (m)]**

#### Extent of Exposure

- Number of days of exposure to study drug will be calculated based on the formula:  
**Duration of Exposure in Days = Treatment Stop Date – (Treatment Start Date) + 1**
- Subjects who were randomized but did not report a treatment start date will be categorised as having zero days of exposure.
- The cumulative dose will be based on the formula:  
**Cumulative Dose = Sum of (Number of Days x Total Daily Dose)**
- If there are any treatment breaks during the study, exposure data will be adjusted accordingly.

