While the adjusted doses did allow observation of a PD response in Cohort 5, the overall single dose data were limited and could not adequately inform a PK/PD model or support informed progression into Part 2 of the study. It was determined to further explore the PK/PD through additional Part 1 cohorts. The purpose of the additional cohorts is to explore dose administration in a manner that should provide a more acceptable PK profile than that observed to date. This includes divided doses to achieve time above the target exposure with varying levels of C_{max} and doses directly related to regimens that may be used in Part 2 of the study. There will be no changes to the current challenge meal or assessments.

3.1.2. Revised Dosing Regimens for Part 2

Based on preliminary PK data from Part 1, the doses and regimens are now better clarified for Part 2. Part 2 Cohorts 1, 2 and 3 will be administered in the AM as divided doses to achieve a daily time above the target exposure with varying levels of C_{max}. Specifically, Cohort 1 will have a regimen of 2 doses separated by 16 hours similar to Part 1 Cohort 8. The purpose is to explore a BID PK profile. Cohorts 2 and 3 will have a regimen of nine hourly doses similar to Part 1 Cohorts 10 and 11. The purpose is to explore PK profiles that approximate a sustained release formulation to guide further dosage development. There will be no changes to the current challenge meal or assessments except for the addition of a skin biopsy outlined in Section 6.4.5.

The regimens are as follows:

Part 2, Cohort 1 would evaluate 10 mg administered twice at time 0h and 16h for a total dose of 20 mg.

Part 2, Cohort 2 would evaluate 27 mg daily administered as 9 doses of 3 mg hourly from time 0 to time 8h daily for 14 days.

Part 2, Cohort 3 would evaluate either 9 mg daily administered as 9 doses of 1 mg hourly from time 0 to time 8h or 45 mg daily as 9 doses of 5 mg hourly from time 0 to time 8h.

Neither the predicted human C_{max}, nor the predicted daily human AUC of evaluated doses is expected to exceed the dog NOAEL exposure of C_{max} (7.73 µg/mL) and AUC(0-t) (111 µg.h/mL).

However, data from a 13-week oral toxicity study in dogs indicate that the NOAEL for dosing duration >28 days will likely be lower than the current NOAEL. While these dog data do not impact the risk for this protocol as they do not change the NOAEL (Section 3.5.1), these data will impact the future viability of certain dose regimens.

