Specifically, **Part 1** doses with PD activity would be progressed into **Part 2**. GI tolerability was not expected to be an issue in **Part 1** and not expected to impact progression into **Part 2**. **Part 2** doses with PD activity and which had tolerability from a GI AE perspective were to be progressed into **Part 3**.

**Part 1** data indicated that single doses of 125 mg or greater were tolerated and had postprandial TG suppression. Divided doses of 45 mg GSK3008356 or greater were tolerated and had postprandial TG suppression. The dose of 45 mg (5 mg hourly for 9 hours) had complete suppression. Divided doses below 45 mg GSK3008356 were not evaluated and exploration of lower divided doses was planned for **Part 2**.

Based on **Part 1** data, the short observed GSK3008356 half-life and future NOAEL identified from a 13 week repeat dose dog toxicology study, **Part 2** initially evaluated placebo or 20 mg GSK3008356 as 10 mg at time 0h and 16h.

Blinded data indicate that 20 mg GSK3008356 divided dosing was not tolerated with 6 of 8 subjects withdrawn early due to GI issues. Dosing was stopped for all subjects before Day 7 of a planned 14 days: 6 due to the GI issues and 2 as the remaining subjects in the cohort were discontinued following discussions between GSK and the Principle Investigator. No PD (postprandial TG suppression) was observed on Day 1; Day 14 could not be evaluated.

Subsequently, placebo or 2 mg GSK3008356 as 1 mg at time 0h and 16h and placebo or 6 mg GSK3008356 as 3 mg at time 0h and 16h were evaluated in Cohorts 2 and 3. All subjects except for 1 in the placebo or 6mg cohort completed the 14 days of dosing, indicating that the doses were tolerated. However, no postprandial TG suppression was observed in either the 2mg or 6mg GSK3008356 divided dosing cohorts.

Based on these data, **Part 2** did not identify a tolerated dose with PD activity and **Part 3** was not initiated.

[figure not shown]
For the purposes of the 204856 RAP, all sections and references pertaining to **Part 3** will be redacted. For any information pertaining to **Part 3** design, objectives and endpoints, please refer to the relevant sections in the protocol. Analysis for **Part 3** is therefore not included in the RAP.

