## 2.4. Study Design

	
75mg, 200mg, 125mg, 200mg divided into 0 hour and 4 hour, 200mg divided into 0 hour and 16 hour, 90mg divided hourly by 9, and 45mg divided hourly by 9, respectively.
 
 
Part 2, 8 subjects receive GSK3008356 (or matching placebo), at a treatment allocation ratio of 6:2, with repeat doses in each of 3 cohorts. The actual doses received are 10mg BID in cohort 1, 1mg BID in cohort 2, and 3mg BID in Cohort 3.
 

--	--

Note: All actual doses start from the morning regardless of the treatment group description.

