### **6.1.4. Drug Exposure**

Exposure will be assessed for Part 1 and Part 2 separately.

For Part 1, the dose received by each subject will be summarized descriptively by cohort of the active treatment.

In Part 2, for each subject, the number of doses, total dose, and the duration (in days) of dosing with the study drug (GSK3008356) will be calculated. These will be listed by subject and summarized descriptively by the cohort active treatment.

The details can be found at [Appendix 12](#): List of Data Displays as well as at the file of the mock shell.

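### SAP 11.6.2 computes cumulative dose from calendar days, so a Part 2 subject who stops between the 0h and 16h doses can be credited with one dose not taken

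*SAP*

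**What the plan says.** Under Extent of Exposure, SAP Section 11.6.2 counts days by date, "Duration of Exposure in Days = Treatment Stop Date – (Treatment Start Date) + 1", and then gives the dose total as "Cumulative Dose = Sum of (Number of Days x Total Daily Dose". One qualification follows: "If there are any treatment breaks during the study, exposure data will be adjusted accordingly".

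SAP Section 6.1.4 promises, for each Part 2 subject, "the number of doses, total dose, and the duration (in days) of dosing with the study drug". It does not say how number of doses or total dose is to be derived. The formula in 11.6.2 is the only rule in the SAP for a dose total.

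On the regimens, Protocol Section 3.1.2 sets Part 2 Cohort 1 at "10 mg administered twice at time 0h and 16h for a total dose of 20 mg". SAP Section 2.4 reports what was given: "The actual doses received are 10mg BID in cohort 1, 1mg BID in cohort 2, and 3mg BID in Cohort 3", with subjects allocated "at a treatment allocation ratio of 6:2" in each cohort. SAP Section 2.2 puts the second dose at 16h in all three cohorts. For Cohort 1 it states: "Dosing was stopped for all subjects before Day 7 of a planned 14 days". In Cohorts 2 and 3 all but one subject finished the 14 days.

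**The concern.** A date-based day count cannot distinguish a last day with one dose from a last day with two. With a split daily dose, multiplying days by the regimen's daily dose credits the 16h dose to anyone who stopped before taking it. The error can only go upward.

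The sentence on treatment breaks does not clearly help. A permanent stop partway through a day is not plainly a break, and no adjustment rule is given.

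What is at stake is the dose received before stopping in the cohort that SAP Section 2.2 describes as not tolerated. That figure describes the cohort; no other planned analysis uses it.

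**Working it through.** **Inputs**
- Unit doses in Part 2: 10, 1 and 3 mg, each given twice a day (SAP 2.4).
- Last dosing day in Cohort 1: 1 to 6, since dosing ended before Day 7 (SAP 2.2).
- Active subjects per cohort: 6 of 8 (SAP 2.4).
- Time of the last dose: not given in either document.

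**The plan's own figure.** 2 × 10 = 20 mg a day, which matches Protocol 3.1.2. Likewise 2 × 1 = 2 mg and 2 × 3 = 6 mg match SAP 2.2. Neither document states a cumulative dose.

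**Per subject.** Let d be the unit dose and k the last dosing day, with the 0h dose on day k the last one taken.
- SAP formula, using the regimen's daily dose: k × 2d.
- Dose taken: (2k − 1) × d.
- Excess: 2kd − (2k − 1)d = d, always one unit dose.

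For Cohort 1 (d = 10 mg):

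| Last day k | Formula (mg) | Taken (mg) | Excess (mg) | Excess (%) |
|---|---|---|---|---|
| 1 | 20 | 10 | 10 | 100 |
| 2 | 40 | 30 | 10 | 33.3 |
| 3 | 60 | 50 | 10 | 20.0 |
| 4 | 80 | 70 | 10 | 14.3 |
| 5 | 100 | 90 | 10 | 11.1 |
| 6 | 120 | 110 | 10 | 9.1 |

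A subject who stops after the 16h dose has no excess.

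**Cohort 1 active-arm mean.** Assume all six active subjects stop on the same day k and m of them stop between doses. The formula mean is 20k, the true mean is 20k − 10m/6, and the excess is 10m/6 mg. Both k and m are assumptions.

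| m of 6 | Excess in mean (mg) | k = 1 | k = 3 | k = 6 |
|---|---|---|---|---|
| 0 | 0 | 0% | 0% | 0% |
| 1 | 1.67 | 9.1% | 2.9% | 1.4% |
| 3 | 5 | 33.3% | 9.1% | 4.3% |
| 6 | 10 | 100% | 20.0% | 9.1% |

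**Where the risk lies.** Early stops in Part 2 were 8 of 8 in Cohort 1 and 1 of 16 in Cohorts 2 and 3 together, so 8 of 9 were in Cohort 1. Since all eight Cohort 1 subjects stopped, all six active subjects did.

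**The other reading.** If Total Daily Dose means the dose taken on each day, the sum is (k − 1) × 20 + 10 mg. That equals the dose taken, and the excess is zero.

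**The case against.** The strongest reply is that the formula does not force the error. It is a sum, and Total Daily Dose is not defined as the nominal dose; read as the dose taken each day, it is exact. This stands. The fault is an undefined term whose ordinary reading overstates the dose, not a formula that must be wrong.

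A second reply is that the SAP already looks to dose received. Section 4 bases the Safety population on treatment or dose actually received, Section 11.5.3 reports by actual treatment, and Section 6.1.4 plans a dose count. This stands in part. Sections 4 and 11.5.3 settle which group a subject belongs to, not how milligrams are summed. The dose count in 6.1.4 is the right quantity, but nothing links it to 11.6.2, and a programmer deriving total dose would find only the date-based formula.

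A reader might infer more than the documents support:
- *That the Cohort 1 figures are in fact biased.* No section gives a last-dose time, so the number who stopped between doses may be zero. The 100% case needs a subject who took only the first dose on Day 1, and none is reported.
- *That all six subjects withdrawn for GI issues are affected.* That count is blinded and may include placebo subjects, who have no active dose to overstate.
- *That the tolerability conclusion is weakened.* In SAP 2.2 it rests on the withdrawals, not on cumulative milligrams.
- *That the divided-dose Part 1 cohorts need the same change.* Section 6.1.4 already summarises the dose each Part 1 subject received.

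**Conclusion.** The point holds as a conditional and minor one. On the ordinary reading of an undefined term, SAP 11.6.2 over-credits a Part 2 subject who stops permanently between the 0h and 16h doses by exactly one unit dose: 10 mg in Cohort 1, 1 mg in Cohort 2 and 3 mg in Cohort 3. For a Cohort 1 subject that is between 9% and 100% of the dose taken, depending on the last dosing day. The effect on the Cohort 1 active-arm mean cannot be fixed from the documents. With everyone stopping on Day 3 it runs from 0% to 20%, according to how many stopped between doses.

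The size rests on two assumptions: that Total Daily Dose is the regimen's daily dose, and that some active subjects stopped between doses. Only the descriptive exposure summary and listing would change. The adverse event, PK and triglyceride analyses do not use cumulative dose.

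**What to change.** For Part 2, define cumulative dose in SAP 11.6.2 as the sum of the doses recorded as administered, that is, number of doses administered × unit dose. State that this is the total dose promised in Section 6.1.4, so that one rule serves both sections. Duration in days can stay as it is. No change is needed for Part 1.

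The cost is a line of text and a cross-reference. There is one thing to check: Protocol Section 5.7 requires the date and time of each in-clinic dose in the source documents, and neither document says that every dose reaches the eCRF. The sponsor should confirm this. Section 6.1.4 already needs a dose count, so the change asks for little that is not already promised.

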**11.6.3. Safety**

ECG Parameters
RR Interval

 
IF RR interval (msec) is not provided directly, then RR can be derived as:                      [1] If QTcF is machine read and QTcF is not provided, then:                     <math display="block">RR = \left[ \left( \frac{QT}{QTcF} \right)^3 \right] * 1000</math> 
 
If ECGs are manually read, the RR value preceding the measurement QT interval should be a collected value THEN do not derive.
 

Corrected QT Intervals

 
When not entered directly in the eCRF, corrected QT intervals by Bazett's (QTcB) and Fredericia's (QTcF) formulas will be calculated, in msec, depending on the availability of other measurements.
 
IF RR interval (msec) is provided then missing QTcB and/or QTcF will be derived as:                     <math display="block">QTcB = \frac{QT}{\sqrt{\frac{RR}{1000}}} \qquad QTcF = \frac{QT}{\sqrt[3]{\frac{RR}{1000}}}</math> 
 

Adverse Events

 
GI AEs/SAEs as specified under SOC as Gastrointestinal (GI)
 

Laboratory Parameters

 
If a laboratory value which is expected to have a numeric value for summary purposes, has a non-detectable level reported in the database, where the numeric value is missing, but typically a character value starting with '<x' or '>x' (or indicated as less than x or greater than x in the comment field) is present, the number of significant digits in the observed values will be used to determine how much to add or subtract in order to impute the corresponding numeric value.                     
 
Example 1: 2 Significant Digits = '< x' becomes x - 0.01
 
Example 2: 1 Significant Digit = '> x' becomes x + 0.1
 
Example 3: 0 Significant Digits = '< x' becomes x - 1
 
 
 

## 11.7. Appendix 7: Premature Withdrawals & Handling of Missing Data

### 11.7.1. Premature Withdrawals

Element	Reporting Detail
General	
 
• Subject study completion is defined in the protocol (Section 4.6) as completing all phases of the study including the follow-up visit. The end of the study is defined as the last subject's last visit.
 
• A subject may withdraw from study treatment at any time at his/her own request, or may be withdrawn at any time at the discretion of the investigator for safety, behavioural or administrative reasons. If a subject withdraws from the study, he/she may request destruction of any samples taken, and the investigator must document this in the site study records. If applicable, the reason for withdrawal of consent. A withdrawn subject may be replaced with another subject who will be assigned to the same treatment randomization. If a subject withdraws from the study, he/she may request destruction of any samples taken, and the investigator must document this in the site study records. Additional subjects/cohorts may be enrolled to allow for evaluation of additional dose levels. All available data from subjects who were withdrawn from the study will be listed and all available planned data will be included in summary tables and figures, unless otherwise specified.
 

### 11.7.2. Handling of Missing Data

Element	Reporting Detail
General	
 
• Missing data occurs when any requested data is not provided, leading to blank fields on the collection instrument: 
 
○ These data will be indicated by the use of a "blank" in subject listing displays. Unless all data for a specific visit are missing in which case the data is excluded from the table.
 
○ Answers such as "Not applicable" and "Not evaluable" are not considered to be missing data and should be displayed as such.
 
 
 

Outliers	
 
• Any subjects excluded from the summaries and/or statistical analyses will be documented along with the reason for exclusion in the clinical study report.
 

#### 11.7.2.1. Handling of Missing Dates

Element	Reporting Detail
General	Partial dates will be displayed as captured in subject listing displays.
Adverse Events	
 
• The eCRF allows for the possibility of partial dates (i.e., only month and year) to be recorded for AE start and end dates; that is, the day of the month may be missing. In such a case, the following conventions will be applied for calculating the time to onset and the duration of the event: 
 
○ Missing Start Day: First of the month will be used unless this is before the
 
 
 

Element	Reporting Detail
	
start date of study treatment; in this case the study treatment start date will be used and hence the event is considered On-treatment as per: Appendix 4 –Treatment States and Phases.
 
 
○ Missing Stop Day: Last day of the month will be used, unless this is after the stop date of study treatment; in this case the study treatment stop date will be used.
 
● Completely missing start or end dates will remain missing, with no imputation applied. Consequently, time to onset and duration of such events will be missing.
 
● Start or end dates which are completely missing (i.e. no year specified) will remain missing, with no imputation applied.
 

